## **Study procedures**

Subjects identified with COPD will be informed about the study and invited to participate by investigators at the time of their routine control visits. All therapies will be prescribed according to the updated National COPD Guidelines (GesEPOC) indicating among other therapies active reduction of risk factors, influenza and pneumococcal vaccination (with PCV13) in all patients with mild, moderate or severe COPD. All the patients will be counselled to stop smoking and advised on life-style modifications. Any vaccination will be prescribed according to clinical practice and not related to the decision to include the subjects in the study. Subjects may be vaccinated before or after inclusion in the study.

Study will include periodic scheduled visits for all patients, to complete a total follow up of 2 years (see Table 1).

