**TABLE 1. FOLLOW UP VISITS**

	Visit	0	1	2	3	4	5
	Month	0	1	6	12	18	24
Verification of inclusion/exclusion criteria		X	X	X	X	X	X
Informed consent signature		X					
Demographic variables		X					
Exacerbations and smoking history		X	X	X	X	X	X
Clinical history (hospital and/or primary care)		X					
Performance or verification of recent spirometry		X			X		X
Completion of QOL test		X			X		X
Treatment and vaccination recommendations adjustment (as per normal clinical practice)		X			X		X
Telephone Follow up (if applicable)				X		X	
PCV13 vaccination record			X		X		X
Influenza vaccination record			X		X		X
Updated treatment record			X		X		X

**Definitions:**

- COPD exacerbations are defined as a complex of two or more respiratory symptoms (worsening dyspnea, cough, sputum production, chest tightness, or wheezing) related to the underlying COPD, with duration of 3 days or more, that require a change in treatment.
  - *Treatment changes* include acute treatment with antibiotics and/or steroids, or an addition of new maintenance bronchodilator.
  - *Mild exacerbations* are those that require new prescription of bronchodilator only
  - *Moderate exacerbations* are those that require antibiotics and/or systemic corticosteroids without hospitalization,
  - *Severe exacerbations* are those that lead to hospitalization.
- The onset date of exacerbations is defined by the onset of the first recorded symptom.
- Exacerbations that occur within 7 days of onset of a prior exacerbation are counted as a single exacerbation

A subject presenting with exacerbation, will be considered as vaccinated at least 15 days after receiving immunization

Redacted

- Immunosuppression:
  - Lymphoma/Leukemia
  - Another neoplasm subjected to immunosuppressing treatments
  - Organ transplant with its corresponding immunosuppressing treatment
  - Leukopenia<1.000/mm; neutropenia<500/mm
  - Patients infected by Human Immunodeficiency Virus (HIV)
  - Congenital immunodeficiency
  - Diseases that requires continuous treatment with systemic corticosteroids administration for more than 14 days (prednisone at doses> 15 mg/day or other equivalent preparations), or cytotoxic agents during the previous six months.

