8.2.3 Effectiveness analysis

8.2.3.1 Study of exacerbations

A detailed analysis of the total number of exacerbations reported by the study patients will initially be performed. The absolute and relative frequency of patients who have reported at least two moderate exacerbations or one severe exacerbation per year (exacerbator patient) will be given.

The following indices will be calculated:

- NEPA (number of exacerbations patient/year) = Total no. of exacerbations reported by patients/ Patient follow-up time^{*)}
- NEPA Mild = Total no. of mild exacerbations/Patient follow-up time
- NEPA Moderate = Total no. of moderate exacerbations/Patient follow-up time
- NEPA Severe = Total no. of severe exacerbations/Patient follow-up time
- NEPA Moderate/severe = Total no. of moderate_severe exacerbations/Patient follow-up time

The following will also be calculated in the subpopulation of exposed patients:

- NEPA_pre_PCV13 = Total no. of exacerbations reported by the patient prior to receiving the PCV13 / Time to vaccination with PCV13^{**)}
- NEPA_pre_PCV13 (moderate/severe) = Total no. of moderate/severe exacerbations reported by the patient prior to receiving the PCV13 / Time to vaccination with PCV13^{**)*)}
- NEPA_post_PCV13 = Total no. of exacerbations reported by the patient after receiving the PCV13 / Time since vaccination with PCV13^{***)}
- NEPA_post_PCV13 (moderate/severe) = Total no. of moderate/severe exacerbations reported by the patient prior to receiving the PCV13 / Time since vaccination with PCV13^{***)}

*) Time from the date of COPD diagnosis to the date of the last follow-up visit. If the date of diagnosis of the disease is unknown, it will be computed as two years before the date of inclusion of the patient in the study

**) Time from date of COPD diagnosis to date of PCV13 vaccination

***) Time from vaccination with PCV13 to date of the last follow-up

Each of the indices calculated above will be described using the main measures of central tendency and dispersion (mean, median, standard deviation, confidence intervals, minimum, maximum and interquartile range).

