The Student's t test, one-way ANOVA or its non-parametric equivalents, the Mann-Mann U test or Kruskal-Wallis H test will be used to determine if statistically significant differences are observed in NEPA, NEPA Mild, NEPA Moderate, NEPA Severe and NEPA Moderate/Severe according to the severity of COPD and type of patient (exposed/unexposed). In order to determine the impact of PCV13 vaccination on exacerbations, paired data comparisons will be made between (NEPA_pre_PCV13 vs. NEPA_post_PCV13) and (NEPA_pre_PCV13 (moderate/severe) vs. NEPA_post_PCV13 (moderate/severe)), using the Student's t-test for paired data or its non-parametric equivalent, the Wilcoxon test.

In order to study which subgroups of patients obtain a greater benefit from vaccination

with PCV13 according to COPD severity, paired data comparisons will be made between (NEPA_pre_PCV13 vs. NEPA_post_PCV13) and (NEPA_pre_PCV13 (moderate/severe) vs. NEPA_post_PCV13 (moderate/severe)), in each of the four patient subpopulations established based on disease severity.

In order to determine the factors associated with the presence of an exacerbator patient, a logistic regression model will be constructed, whose dependent variable is (exacerbator/non-exacerbator patient) and, as independent variables, all those possible factors that have been significant in the univariate models ($p_{value} < 0.25$), following the methodology of Hosmer-Lemeshow.

- ❖ Vaccine exposure (PCV13 yes/no)
- ❖ COPD severity (Grade I, Grade II, Grade III, Grade IV)
- ❖ Age
- ❖ Sex
- ❖ Time since diagnosis of the disease
- ❖ Patient with stable treatment for at least three months
- ❖

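### SAP post-PCV13 exacerbation rates start on the day of vaccination, whereas the protocol counts a patient as vaccinated only from 15 days after the dose

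*SAP*

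**What the plan says.** The protocol (8.3.1, definitions under Table 1) places this rule among the exacerbation definitions: "A subject presenting with exacerbation, will be considered as vaccinated at least 15 days after receiving immunization".

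SAP 8.2.3.1 defines the rates for vaccinated patients without that rule:

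- Pre-PCV13 time: "Time from date of COPD diagnosis to date of PCV13 vaccination".
- Post-PCV13 time: "Time from vaccination with PCV13 to date of the last follow-up".
- Post-PCV13 index, all exacerbations: "Total no. of exacerbations reported by the patient after receiving the PCV13 / Time since vaccination with PCV13".
- Post-PCV13 index, moderate/severe: "Total no. of moderate/severe exacerbations reported by the patient prior to receiving the PCV13 / Time since vaccination with PCV13". The numerator refers to events before the vaccine, an apparent copy error.

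The same section gives the use of these indices: "In order to determine the impact of PCV13 vaccination on exacerbations, paired data comparisons will be made between" the pre and post rates, first in all vaccinated patients and then within each of the four COPD severity grades.

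Elsewhere in the SAP (5.4, 8.2.1 and the logistic model in 8.2.3.1), exposure is a plain vaccinated/not vaccinated split. The timing of the dose is not fixed: "Subjects may be vaccinated before or after inclusion in the study" (Protocol 8.2, Study procedures).

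**The concern.** The two documents draw the line between unvaccinated and vaccinated at different points. For the first 15 days after the dose (days 0 to 14), the protocol does not yet regard a patient with an exacerbation as vaccinated, while the SAP treats those days as post-vaccination. The SAP neither mentions nor justifies the departure.

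At stake is the paired pre/post comparison, through which the SAP addresses both primary objectives. If the vaccine gives no protection in the first two weeks, those days pull the post-vaccination rate back towards the pre-vaccination rate. Two programmers could also reasonably compute different rates, one following the SAP footnote and the other the protocol definition.

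**Working it through.** No sample size, power or rate stated in the plan depends on the 15-day rule, so there is no plan figure to reproduce. The check compares the texts and then sizes the gap.

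**1. Where days 0 to 14 fall**

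| Item | Protocol rule | SAP 8.2.3.1 |
|---|---|---|
| Event in days 0–14, all-exacerbation index | not yet vaccinated | post-PCV13 |
| Event in days 0–14, moderate/severe index | not yet vaccinated | not in the post numerator as worded (copy error); post if corrected |
| Time in days 0–14, both indices | not stated; follows from the event rule | post-PCV13 |

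The protocol rule is worded for events. It extends to time because a rate needs its numerator and denominator on the same window.

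**2. Share of post-vaccination time affected**

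f = 15 / post-vaccination days, at 365.25 days per year:

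- 24 months: 15/730.5 = 2.1%
- 12 months: 15/365.25 = 4.1%
- 6 months: 15/182.6 = 8.2%

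**3. Effect on a rate ratio**

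Input: the one-year risks of 27% and 37% in Protocol 8.5. Converted to rates, ln(0.73)/ln(0.63) = 0.68.

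Assumptions: constant event rate, no protection in days 0–14, full effect afterwards. The ratio under the SAP definition is then f × 1 + (1 − f) × 0.68 = 0.68 + 0.32f.

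- 24 months: 0.68 + 0.32 × 0.0205 = 0.687
- 12 months: 0.68 + 0.32 × 0.0411 = 0.693
- 6 months: 0.68 + 0.32 × 0.0821 = 0.706
- 30 days: 0.68 + 0.32 × 0.50 = 0.84

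**4. If the rule is applied to events only**

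If the 15-day rule is taken over from the protocol for events while the SAP time footnote stands, the post rate loses the events of days 0–14 but keeps the time. The ratio becomes 0.68 × (1 − f): 0.666, 0.652 and 0.624 at 24, 12 and 6 months. The error then runs the other way and flatters the vaccine.

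**5. Number of patients concerned**

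Protocol 8.5 gives 540 vaccinated patients and a 37% yearly control risk.

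- Linear: 540 × 0.37 × 15/365.25 = 8.2
- Exponential: 540 × [1 − exp(ln(0.63) × 15/365.25)] = 540 × 0.0188 = 10.1

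About 8 to 10 patients would have a first moderate/severe exacerbation in days 0–14.

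**6. Very short windows**

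The indices are computed per patient and then summarised. A patient whose follow-up ends within 15 days of the dose has no vaccinated time under the protocol rule. Under the SAP, one event gives that patient a post rate of at least 365.25/15 = 24 per year, enough to disturb a mean or a paired t-test.

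**The case against.** The best defence is that the SAP relies on the protocol for definitions. It does not restate the protocol's mild/moderate/severe definitions or its rule for merging exacerbations within 7 days, so the 15-day rule may be meant to carry over too. Protocol 8.7 also lets the SAP modify the protocol's plans and reserves amendments for major changes. This has some force for event counts. It does not rescue the time footnote, which explicitly starts at vaccination; step 4 shows what follows if only the events are lagged.

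Three further points stand and limit the concern.

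- **Size.** Follow-up is planned for two years and some patients are vaccinated before inclusion, so many post-vaccination windows may be long. The documents do not show that short windows are typical.
- **Direction.** A reader might infer that the SAP necessarily dilutes the vaccine effect. That needs a constant event rate and no early protection, neither of which the documents state. If vaccination is deferred around acute episodes (an assumption), few events would fall in days 0–14, and including those days could exaggerate the benefit.
- **Exposed status.** For a yes/no label, the lag changes only patients whose follow-up ends within 15 days of the dose. The between-group NEPA runs from COPD diagnosis to the last visit, so it already includes vaccinated patients' pre-vaccination time; a 15-day rule does not alter that.

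**Conclusion.** The inconsistency is real and touches the analysis used for the primary objectives. On average it is small: about 0.01 on the rate ratio for 12 to 24 months of post-vaccination time and about 0.03 at 6 months, under the assumptions in step 3. It matters more for patients vaccinated shortly before their last visit.

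Two stronger readings are not supported. One is that all exacerbations in days 0–14 are attributed to the vaccine. As worded, that is true of the all-exacerbation index only: the moderate/severe numerator refers to events before vaccination, and only its denominator includes those days. The other is that this gap alone could overturn the study's result; the figures for long follow-up do not show that. The case for correcting it is that a rule set in advance has been dropped without explanation and costs little to restore.

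**What to change.** In SAP 8.2.3.1:

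1. Start both the events and the time of the two NEPA_post_PCV13 indices 15 days after PCV13.
2. State one rule for days 0–14: count them as pre-PCV13, which follows the protocol wording, or exclude them from both periods. Apply it to numerator and denominator alike.
3. State that patients with fewer than 15 days of follow-up after the dose have no post-PCV13 rate and are not classed as exposed.
4. Correct the moderate/severe post-PCV13 numerator separately, since it now refers to events before vaccination.

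If the sponsor prefers no lag, the SAP should say so with reasons, and the sponsor should decide whether Protocol 8.7 then calls for an amendment.

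Assigning days 0–14 to unexposed time in a between-group model is not an option here. The SAP compares patient-level rates and fits a logistic model with PCV13 yes/no; it has no time-varying exposure model.

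The change is to wording and derivation rules. It costs about two weeks of post-vaccination time per vaccinated patient, at most 540 × 15/365.25 = 22 person-years across the planned cohort.

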### **8.2.1. Inclusion criteria**

Patients must meet all of the following inclusion criteria to be eligible for inclusion in the study:

1. Patient  $\geq 18$  years diagnosed with COPD (any stage, the subgroups for the analysis would be based on COPD severity grade)

Redacted

2. Evidence of a personally signed and dated informed consent document indicating that the patient (or a legally acceptable representative) has been informed of all pertinent aspects of the study.
3. Ability to understand and complete the required QoL questionnaires
4. At least 2 years of clinical history available that includes records of previous moderate/severe exacerbations, influenza and pneumococcal vaccination history comorbidities and previous treatments.
5. Spirometry data\* (maximum 6 months old, or if not available at enrollment, to be performed as per normal clinical practice at visit 1 +/- one month)

\*Subjects with FEV1 <40 should be less than 20% of the total study population (related to the microbiological etiology dependent on severity)

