### **8.3. Variables**

**Variables to be recorded from previous clinical history and follow up visits (according to Table 1):**

- Consent date
- Subject code
- Demographic and epidemiological data;
- Antropometric data (weight, height, body mass index (BMI), Waist Circumference)
- Smoking habit, alcohol consumption
- Spirometric data (FEV1, FVC, FEV1/FVC)
- Pharmacological treatment
- COPD severity (GOLD)
  - o GRADE 1: Mild/unknown [FEV1≤ 80%, FEV1/FVC < 0,7 or no spirometry data]
  - o GRADE 2: Moderate [50% ≤ FEV1< 80%,FEV1/FVC < 0,7]
  - o GRADE 3: Severe [30% ≤ FEV1 < 50%, FEV1/FVC < 0,7]
  - o GRADE 4: Very severe [FEV1< 30% o FEV1< 50% plus respiratory failure,FEV1/FVC < 0,7]
- Number and severity of exacerbations

Redacted

- Frequency of total exacerbations (moderate and severe) in the previous year and during follow-up (recorded at hospital or primary care level).
- Comorbidities
  - o high blood pressure
  - o dyslipidemia
  - o type 2 diabetes mellitus
  - o metabolic syndrome
  - o heart failure
  - o ischemic heart disease
  - o chronic kidney disease
  - o cirrhosis
- History of neoplasia (solid organ and hematologic)
- Pneumococcal vaccination
- Influenza vaccination
- QoL questionnaire (reduced SGRQ, CAT) - completed by subjects and transcribed into electronic case report form (CRF)

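### SAP 8.2.3.1 answers both primary objectives with before/after tests in vaccinated patients only; no controlled analysis is designated for objective 1 and no PCV13-by-grade test is specified for objective 2

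*SAP*

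**What the plan says.** The primary objectives (Protocol 7, SAP 2.2) are the effect of PCV13 on moderate/severe exacerbations over two years, and which COPD severity group benefits most. Protocol 8.1 and SAP 8.1 describe a cohort study with unvaccinated participants as comparator. Protocol 8.5 and SAP 5 size it as about 540 vaccinated against 1000 unvaccinated.

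SAP 8.2.3.1 introduces the pre- and post-vaccination rates with "The following will also be calculated in the subpopulation of exposed patients". It then says "In order to determine the impact of PCV13 vaccination on exacerbations, paired data comparisons will be made between" those two rates, by paired t-test or Wilcoxon test. To find which severity groups benefit more, it repeats the paired comparison "in each of the four patient subpopulations established based on disease severity".

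On the indices themselves:
- The moderate/severe post-vaccination index is printed as "NEPA_post_PCV13 (moderate/severe) = Total no. of moderate/severe exacerbations reported by the patient prior to receiving the PCV13 / Time since vaccination with PCV13".
- Pre-vaccination time is "Time from date of COPD diagnosis to date of PCV13 vaccination". Time for the overall rate is "Time from the date of COPD diagnosis to the date of the last follow-up visit", starting two years before inclusion if the diagnosis date is unknown.
- Protocol 8.2.1 requires "At least 2 years of clinical history available that includes records of previous moderate/severe exacerbations". Protocol 8.3 lists "Frequency of total exacerbations (moderate and severe) in the previous year and during follow-up", while SAP 6 speaks of previous years.
- Protocol 8.7 defines impact over another window: two years after inclusion against two years before it.

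**The concern.** The tests whose stated purpose matches the two primary objectives make no use of the roughly 1000 unvaccinated patients. A before/after difference within vaccinated patients contains any vaccine effect plus time trend, disease progression, changes in other care, and regression to the mean if vaccination tends to follow a bad spell. Nothing in the test separates these.

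The bias can run either way. A falling background rate looks like benefit. Event records that do not reach back to diagnosis make the pre-vaccination rate too low and look like harm. Because no controlled analysis is named for objective 1, the study's answer would depend on which of several results is put forward. Objective 2 has no controlled answer at all.

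**Working it through.** **1. What the study is sized for.** Year-1 inputs (SAP 5): 378 vaccinated at 27%, 700 unvaccinated at 37%, two-sided 0.05 (sidedness assumed).
- Pooled proportion = (378×0.27 + 700×0.37)/1078 = 0.335.
- SE under the null = √[0.335×0.665×(1/378 + 1/700)] = 0.0301.
- SE under the alternative = √[0.27×0.73/378 + 0.37×0.63/700] = 0.0292.
- Power = Φ[(0.10 − 1.96×0.0301)/0.0292] = Φ(1.40) = 91.9%, against 91.43% stated.

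The figure reproduces, as a comparison of proportions between two cohorts. It says nothing about a paired test in one cohort. (The two-year row gives 97.5% against 91% stated; that is a separate matter.)

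**2. Where controls are used.**
- SAP 8.2.3.1 tests overall rates by exposure. The test is unadjusted, names no objective, and uses time from diagnosis, so it mixes pre- and post-vaccination time.
- SAP 8.2.3.1 has a logistic model for exacerbator status. Its purpose is associated factors, and candidate variables, PCV13 among them, are screened at p<0.25.
- SAP 8.1 has a logistic model for any exacerbation during the study. PCV13 enters, but the purpose is again associated factors, follow-up time is ignored despite assumed 30% losses per year, and confounders are only to be considered.
- SAP 9, table 3.2.1, lists change in exacerbations by exposed/unexposed, with no test attached.

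None is designated for objective 1. SAP 8.2.1 and SAP 9 split by exposure and by grade separately; no test of PCV13 by grade appears.

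**3. The printed index.** With E events before vaccination, the pre index is E/T_pre and the printed post index is E/T_post. Their ratio is T_pre/T_post whatever the vaccine does: 5/2 = 2.5 for five and two years.

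**4. Unmatched windows.** Suppose the true rate is λ, the true rate ratio is 0.70, and only the last 2 of T years before vaccination are recorded. Then pre = 2λ/T, post = 0.70λ, and the ratio is 0.70×T/2. That gives 1.05 for T = 3 and 1.75 for T = 5, so a 30% reduction appears as a 5% or 75% increase.

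**5. Simulations (illustrative).** The documents do not give trend, dispersion, record completeness or grade split. Assumed: gamma-Poisson counts with shape k = 0.5, 1 or 2; mean set so that P(at least one event in a year) = 0.37, i.e. k(0.63^(−1/k) − 1) = 0.760, 0.587 or 0.520 per year; two years of follow-up; no vaccine effect unless stated.
- No trend, complete records: paired t-test false benefit 2–3%.
- 10% fall in both groups, two-year pre-period: false benefit about 40–52% with 540 vaccinated, about 21–30% with 264. A comparison of change against controls stays at about 5%.
- Diagnosis five years back, k = 1, records cut to two years in 10% or 20% of patients: false harm about 24% or 72% by t-test. By Wilcoxon it is about 6% or 42% (37% in a repeat run of the 20% case).
- Objective 2, identical 30% reduction in every grade, split 15/45/30/10%, k = 1: the four paired tests disagree on significance in about 80% (540) or 91% (264) of studies.

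**The case against.** **Controlled analyses exist.** SAP 8.1 says results will be evaluated as a cohort study, and its yes/no model resembles the outcome used for sample size. A reader might infer that the plan ignores its controls; it does not. The gap is that no controlled analysis is designated, while the paired tests carry the wording of the objectives.

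**A paired test removes stable confounding.** This stands. Suppose 45% of patients above the median underlying rate are vaccinated and 25% below it, with complete records and no trend. The paired test then keeps 2–3% error each way and change-versus-controls is also clean. A model adjusted for prior events shows a spurious rate ratio of 1.16–1.17, with false harm in 68–80% of studies. If vaccination instead follows recent events (45% against 25%), the ranking reverses: the adjusted model gives false benefit of 1–2% and false harm of 2–6%, the paired test gives false benefit of 26–74%, and change-versus-controls 42–90%. Neither mechanism is documented, so no single model can be called the right one.

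**Records may go back far enough.** Two years is a minimum, Protocol 8.2 expects data from earlier years, and the two-year fallback roughly matches the required history. Near-certain false harm follows only if everyone's records stop at two years, which the documents do not say.

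**Co-intervention is routine.** Smoking advice and treatment review (Protocol 8.2, Table 1) may also have occurred before vaccination, so the 10% fall is an assumption.

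**The numerator looks like a copying slip.** Probably so, since the all-exacerbation index above it counts events after vaccination. It still has to be corrected.

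**The SAP does not say that greatest benefit is judged by significance.** True, but it names no other between-grade comparison.

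**Conclusion.** The point holds. For both primary objectives the SAP's stated tests are uncontrolled, no controlled analysis is designated for objective 1, and objective 2 has no comparison of effect between grades. If followed as printed, the moderate/severe paired test is meaningless. These findings rest on the text alone.

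The sizes rest on the assumptions in step 5 and depend on the test used. They show that modest departures matter; they do not forecast this study. Two stronger readings fail. One is that the plan is biased towards the vaccine: the direction cannot be known beforehand. The other is that one adjusted regression would settle the question: it can fail where a paired or change comparison holds. Protocol 8.7 also uses a before/after contrast, so both documents need attention.

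**What to change.** 1. Designate for objective 1 one exposed-versus-unexposed analysis of moderate/severe exacerbations during follow-up. Force PCV13 into the model, account for person-time, and count exposure from day 15 after vaccination, as in the Protocol 8.3.1 definitions. Adjust for GOLD grade, influenza vaccination, smoking, age, site and prior exacerbation count over one fixed window. A negative binomial model with a person-time offset would serve.
2. Pre-specify as sensitivity analysis a comparison of pre/post change in exposed versus unexposed patients over equal recorded windows, and report any disagreement with the primary result. State a sensitivity analysis for patients vaccinated before inclusion.
3. Answer objective 2 with a PCV13-by-grade interaction or trend test and grade-specific effects with 95% confidence intervals.
4. Correct the moderate/severe post-vaccination numerator to events after vaccination, take events and time from the same recorded window, and reconcile Protocol 8.7 with SAP 8.2.3.1.
5. Present exposed-only paired results as supportive, and the overall result as an adjusted association.

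The cost is SAP wording, modest programming and possibly a protocol amendment (Protocol 8.7). The database must hold two years of dated events. Residual confounding remains. Power for objective 2 is limited and should be stated: for assumed rate ratios of 0.6/0.7/0.85/1.0 across grades, the four-grade test has 47–53% power with 540/1000 patients and 24–28% with 264/490; the trend test has 64–70% and 37–41%.
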